10.2.4 Hospitalization for the management of any of the above expected events

10.3 Abnormal hematologic values will not be recorded on the case report form. For abnormal chemical values, the apogee or nadir (whichever is appropriate) will be reported per course on the case report form.

10.4 Serious Adverse Event Reporting (SAE)

An adverse event or suspected adverse reaction is considered “serious” if, in the view of either the investigator or the sponsor, it results in any of the following outcomes:

- Death
- A life-threatening adverse drug experience – any adverse experience that places the patient, in the view of the initial reporter, at immediate risk of death from the adverse experience as it occurred. It does not include an adverse experience that, had it occurred in a more severe form, might have caused death.
- Inpatient hospitalization or prolongation of existing hospitalization
- A persistent or significant incapacity or substantial disruption of the ability to conduct normal life functions.
- A congenital anomaly/birth defect.

Important medical events that may not result in death, be life-threatening, or require hospitalization may be considered a serious adverse drug experience when, based upon appropriate medical judgment, they may jeopardize the patient or subject and may require medical or surgical intervention to prevent one of the outcomes listed in this definition. Examples of such medical events include allergic bronchospasm requiring intensive treatment in an emergency room or at home, blood dyscrasias or convulsions that do not result in inpatient hospitalization, or the development of drug dependency or drug abuse (21 CFR 312.32).

- Important medical events as defined above, may also be considered serious adverse events. Any important medical event can and should be reported as an SAE if deemed appropriate by the Principal Investigator or the IND Sponsor, IND Office.
- All events occurring during the conduct of a protocol and meeting the definition of a SAE must be reported to the IRB in accordance with the timeframes and procedures outlined in “The University of Texas M. D. Anderson Cancer Center Institutional Review Board Policy for Investigators on Reporting Unanticipated Adverse Events for Drugs and Devices”. Unless stated otherwise in the protocol, all SAEs, expected or unexpected, must be reported to the IND Office, regardless of attribution (within 5 working days of knowledge of the event).

- **All life-threatening or fatal events**, that are unexpected, and related to the study drug, must have a written report submitted within **24 hours** (next working day) of knowledge of the event to the Safety Project Manager in the IND Office.
- Unless otherwise noted, the electronic SAE application (eSAE) will be utilized for safety reporting to the IND Office and MDACC IRB.
- Serious adverse events will be captured from the time of the first protocol-specific intervention, until 30 days after the last dose of drug, unless the participant withdraws consent. Serious adverse events must be followed until clinical recovery is complete and laboratory tests have returned to baseline, progression of the event has stabilized, or there has been acceptable resolution of the event.
- Additionally, any serious adverse events that occur after the 30 day time period that are related to the study treatment must be reported to the IND Office. This may include the development of a secondary malignancy.

Reporting to FDA:

- Serious adverse events will be forwarded to FDA by the IND Sponsor (Safety Project Manager IND Office) according to 21 CFR 312.32.

It is the responsibility of the PI and the research team to ensure serious adverse events are reported according to the Code of Federal Regulations, Good Clinical Practices, the protocol guidelines, the sponsor's guidelines, and Institutional Review Board policy.

Investigator Communication with Supporting Company:

Serious adverse event will be reported by FAX concurrently to OSI Drug Safety ([contact]). Information not available at the time of the initial report (e.g., an end date for the adverse event or laboratory values received after the report) must be documented on a follow-up report. A final report to document resolution of the SAE is required. **Hospitalizations for the management of any expected adverse events (previously described) will not have an expedited report but it will be included in the annual report via the SAE log.**

Pregnancies: Any pregnancy that occurs during study participation or within 4 weeks of the patient's last study drug administration should be reported using the MD Anderson SAE Form. To ensure patient safety each pregnancy must also be reported to OSI and the IND Office within 24 hours of learning of its occurrence.

The Investigator will follow the pregnant female until completion of the pregnancy. The Investigator will provide this information as a follow-up to the initial SAE.

If the outcome of the pregnancy meets the criteria for immediate classification as a SAE (i.e., spontaneous abortion [any congenital anomaly detected in an aborted fetus is to be documented], stillbirth, neonatal death, or congenital anomaly), the Investigator should follow the procedures for Expedited Reporting of SAEs.

11.0 STATISTICAL CONSIDERATIONS¹⁷

This is an open-label, to assess the efficacy and safety of erlotinib in patients with AML. The primary efficacy endpoint is overall response as defined in section 9.3.

The historical experience in this patient population is that response with standard therapy, when available, is less than 1%. In many instances (eg, patients with myelodysplastic syndrome failing hypomethylating agents), no standard therapy is even available. Thus, an overall response rate of 20% will be considered significant. For the purpose of this analysis, a response will be considered if occurring after 3 months of therapy (or earlier).

The Simon's optimal two-stage design will be used to implement the study. A total of 29 patients will be enrolled to this study. These sample sizes are based on Simon's optimal 2-stage designs of alpha=0.05 with power of 95% (beta=0.05) to test the null hypothesis that the ORR will be $\leq 1\%$ versus the alternative hypothesis that ORR will be ≥ 20 . At the first stage, 14 patients will be enrolled. If no response is observed among the 14 patients, the trial will be terminated early for futility. If one or more patients have response, 15 more patients will be enrolled at the 2nd stage. If at least 2 responses achieved after the completion of the 2nd stage, the study will conclude that the treatment improves the response rate from 1% to 20%. The probability of early termination under the null hypothesis is 87%. The probability of seeing at least 2 responses under the null (ORR = 1%) is 3% while the probability of seeing at least 2 with an event rate of 20% is 94.8%.

Further enrollment will continue during the interim analysis unless no responders (CR+PR+HI) have been reported by the time of enrollment of the 14th subject being analyzed. In this event, enrollment will be suspended and these 14 subjects will be followed to further assess their responses. During this follow-up period, as soon as one response is observed, enrollment will resume. If no response is observed after the 14 subjects have been fully assessed, the trial will be terminated for futility.

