3.0 STUDY DESIGN

- This will be a phase II, single-arm, open-label study.
- All patients will receive therapy with erlotinib administered orally as a continuous daily dose in 28-day cycles. Patients will continue therapy until clinically significant progression of the disease or unacceptable toxicity.
- The historical experience in this patient population is that response with standard therapy, when available, is less than 1%. In many instances (eg, patients with myelodysplastic syndrome failing hypomethylating agents), no standard therapy is even available. Thus, an overall response rate of 20% will be considered significant.

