11.2 Statistical Analysis

The primary efficacy endpoint is the overall response (ORR) as assessed by investigators and defined in section 9.3. The overall response rate (ORR) will be calculated for Using the intent-to-treat (ITT) data. The corresponding 95% confidence interval will be derived.

Safety summaries will include tabulations in the form of tables and listings. The frequency (number and percentage) of treatment-emergent AEs will be reported.

Additional AE summaries will include AE frequency by AE severity and by relationship to study drug. Adverse events requiring discontinuation of study drug will be summarized separately, both overall and by AE severity and by relationship to study drug. Subjects found to have abnormal values considered clinically significant will be summarized. Laboratory shift tables containing counts and percentages will be prepared by laboratory parameter and time. Summary tables will be prepared for each laboratory parameter. Figures of changes in laboratory parameters over time will be generated.

Subject demographics (including age, sex, and race/ethnicity) and other baseline characteristics (including ECOG performance status, disease burden, and number of prior therapies) will be summarized. Summary statistics will include: means, standard deviations, and medians for continuous variables and proportions for categorical variables.

For secondary endpoints, descriptive statistics will be used to summarize the expression of biomarkers and the concentrations of plasma erlotinib. The Wilcoxon rank sum test will be used to compare the expressions of biomarkers and concentrations of plasma erlotinib between patients with and without response.

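### Section 11.0 fixes the conclusion that response improves to 20% once 2 of 29 patients respond, but that result rejects only a response rate of 1% or less

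*Combined protocol and SAP*

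**What the plan says.** Section 11.0 of the combined protocol and SAP sets out the primary efficacy test. "The Simon's optimal two-stage design will be used to implement the study". The design is "to test the null hypothesis that the ORR will be" at most 1%, "versus the alternative hypothesis that ORR will be" at least 20%, with alpha 0.05 and power 95%. Fourteen patients enter stage 1, and the trial stops if none responds. Otherwise 15 more are enrolled, 29 in total. With at least 2 responses at the end, "the study will conclude that the treatment improves the response rate from 1% to 20" percent.

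The section gives an early-termination probability of 87% under the null hypothesis and a 3% chance of at least 2 responses at an ORR of 1%. It adds that "the probability of seeing at least 2 with an event rate of 20% is 94.8" percent.

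Two other statements bear on how the conclusion will be read. Section 3.0 says, and Section 11.0 repeats: "Thus, an overall response rate of 20% will be considered significant". Section 11.2 plans the ORR on the intent-to-treat data and adds: "The corresponding 95% confidence interval will be derived".

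**The concern.** The two rates in a Simon design have different roles. The 1% is the hypothesis that a positive result rejects. The 20% is the rate at which the design was given enough power. A positive result is evidence against the first and does not demonstrate the second. Section 11.0 nevertheless writes the second into the conclusion as an effect size.

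This is the plan's only statement of what a positive primary result means. Because 20% is also the rate the plan calls significant, a reader may take the conclusion to say that the target was reached. The trial has a single arm, so that sentence may well be what readers carry forward. The trial's conduct, the go/no-go decision and the estimate are not affected; the pre-specified claim on the primary endpoint is.

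**Working it through.** **Inputs (Section 11.0).** Stage 1: n1 = 14, stop at 0 responses. Stage 2: n2 = 15, N = 29. Rule met if the total is at least 2. Null ORR 1%, alternative 20%.

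**Formula.** The rule fails if there is no response in stage 1, or exactly one in stage 1 and none in stage 2. For a true ORR p:

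P(rule met) = 1 − (1−p)^14 − 14p(1−p)^28

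**Step 1: reproduce the plan's figures.**
- Early stop at 1%: 0.99^14 = 0.8687 (plan: 87%).
- Rule met at 1%: 1 − 0.8687 − 0.1057 = 0.0256 (plan: 3%).
- Rule met at 20%: 1 − 0.0440 − 0.0054 = 0.9506 (plan: 94.8%).

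A search over two-stage designs with type I error at most 0.05 and power at least 95% returns this same design as optimal. The design is therefore sound. The gap between 94.8% and 95.1% is immaterial here.

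**Step 2: what the rule rejects.** Solving 1 − (1−p)^14 − 14p(1−p)^28 = 0.05 gives p = 0.0145. At one-sided 5%, meeting the rule therefore rejects true rates up to about 1.45%. This describes the rule as a whole; a particular result with many more responses would support a higher lower bound.

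**Step 3: observed ORR at and above the boundary.**

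| Responses of 29 | Observed ORR |
|---|---|
| 2 | 6.9% |
| 3 | 10.3% |
| 4 | 13.8% |
| 5 | 17.2% |
| 6 | 20.7% |

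Six responses is the first count with an observed ORR of at least 20%. A two-sided exact 95% interval with its lower limit above 20% needs 11 of 29 (37.9%, lower limit 20.7%). At 2 of 29 the ordinary exact 95% interval, ignoring the two-stage sampling, is 0.8% to 22.8%.

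**Step 4: how often the rule is met below 20%.** The plan gives no expected ORR other than the 20% alternative, so 5% and 10% are assumptions for illustration. The third column is the probability of passing stage 1 and ending with 2 to 5 responses.

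| True ORR | P(rule met) | P(rule met with 2 to 5 responses) | Share of positive trials |
|---|---|---|---|
| 5% | 0.3458 | 0.3431 | 0.3431/0.3458 = 99% |
| 10% | 0.6980 | 0.6348 | 0.6348/0.6980 = 91% |
| 20% | 0.9506 | 0.4167 | 0.4167/0.9506 = 44% |

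The first two rows show how readily the rule is met when the true rate is far below 20%. The last row is sampling variation around a true 20%. In those trials the conclusion would happen to be correct although the estimate lies below it, so 44% is not a rate of wrong conclusions.

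**The case against.** The strongest reply is that the sentence is shorthand. Section 11.0 names the two hypotheses shortly before it and gives the chance of 2 or more responses at exactly those two rates just after it. In that setting the phrase can be read as deciding for the alternative over the null, and nothing says 20% will be reported as the estimated rate. Section 11.2 obtains the estimate and its interval separately. The remark that 20% will be considered significant can be read as explaining the choice of target only.

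The shorthand reading is plausible, but no text in Section 11.0 or 11.2 limits the conclusion to rejection of 1%, and the sentence as written names an effect size. The planned estimate and interval would stand beside the conclusion; they do not replace it.

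Two parts of the reply stand. First, the interval need not conflict with 20%. Section 11.2 names no method, and the exact interval at 2 of 29 reaches 22.8%. It fails to establish 20% but does not exclude it; the clear mismatch is with the point estimate. Second, that same exact interval starts at 0.8% and so contains 1%. Rejection at 2 of 29 rests on the one-sided two-stage test, and rewording the conclusion does not remove this tension.

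**Conclusion.** The concern holds: the sentence is wrong as written. If followed, it would announce an improvement to 20% on results as low as 6.9%, when meeting the rule excludes only rates up to about 1.45% at one-sided 5%. With assumed true rates of 5% and 10%, the trial would reach that conclusion with probability 0.35 and 0.70.

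The calculations assume independent responses with a common rate and the stated stopping rule. The design figures, the boundary values and the 1.45% do not depend on the illustrative rates. The matter is minor because it lies in one sentence and leaves the design, error rates, decision rule and estimate intact.

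**What to change.** Replace the concluding sentence in Section 11.0 with wording such as: *If at least 2 responses are observed after stage 2, the null hypothesis ORR ≤ 1% is rejected; this does not establish an ORR of 20%, which is the design alternative. The size of the effect will be judged from the estimated ORR and its confidence interval.*

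It would help to add that the rejection rests on the one-sided two-stage test, since an ordinary two-sided exact 95% interval at 2 of 29 includes 1%.

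The change costs one sentence, or two with that addition. Sample size, boundaries, enrolment and the planned estimate and interval stay as they are. The price is a less favourable headline claim.

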11.1 Safety Monitoring

Toxicities will be monitored using the method of Thall, Simon, and Estey [1]. Toxicity is defined as clinically significant, non-hematologic grade 3 or 4 toxicities at least possibly related to erlotinib. We would like to control the rate of clinically significant, non-hematologic grade 3 or 4 toxicities at least possibly

related to erlotinib to be lower than 30% during the 1st 28 days. Using this information a non-informative flat prior distribution of Beta (0.6, 1.4) was chosen for the new combination treatment.

The interim monitoring will be first conducted after the first 10 patients have been evaluated and then be repeated continuously. The monitoring rule for toxicity is $\Pr(\theta_{E, \text{Tox}} > 0.3 | \text{data}) > 0.90$, where $\theta_{E, \text{Tox}}$ is the proportion of any grade 3 or 4 clinically significant, non-hematologic toxicities at least possibly related to erlotinib. That is, the trial will be terminated if at any time during the study there is a more than 90% chance that the average rate of grade 3 or 4 non-hematologic adverse events is more than 30%.

The stopping boundaries, based on these assumptions and monitoring conditions are shown in Table 1. For example, accrual will be stopped if 6 or more patients experience toxicity among the first 10 patients treated or if 7 or more patients experience toxicity in the first 13 patients.

Table 1: Stop accrual if the number of grade 3 or 4 non-hematologic adverse events is equal to or greater than indicated (i.e., # Grade 3 or 4 toxicity) among the number of patients accrued (i.e., # Patients)

# Grade 3 or 4 toxicity	6	7	8	9	10	11	12
# Patients	10	13	15	18	21	23	26

Table 2 shows the operating characteristics for this stopping rule based on 10000 simulations.

Table 2: Operating characteristics of toxicity monitoring (Based on 10000 simulations)

True Toxicity Probability	Stop Probability	Trial Sample Size Percentile		
		25%	50%	75%
0.2	3%	29	29	29
0.3	21.50%	29	29	29
0.4	57.50%	11	22	29
0.5	88.50%	10	11	19

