2.1.1 Adverse Events

As of 15 November 2010, more than 33,000 healthy subjects and cancer patients have participated in company-sponsored and investigator-

sponsored studies; more than 22,000 of these subjects or patients are estimated to have received erlotinib.

The Global Drug Safety Database contains approximately 9243 unique clinical study serious adverse events assessed as related to erlotinib in a total of 5846 patients (see table below).

MeDRA System Organ Class Preferred Terms	Fatal Events	Total Events
Infections and infestations		
Pneumonia, pneumonia primary atypical, lung infections, upper/lower respiratory tract infection, bronchitis	56	230
Cellulitis, infection, abscess, localized infection, folliculitis, skin infection	8	137
Sepsis, staphylococcal sepsis, bacteremia, sepsis syndrome	26	64
Neutropenic sepsis	2	5
Pharyngitis, herpangina, tonsillitis	-	4
Cellulitis orbital	-	1
Endometritis	-	1
Blood and lymphatic system disorder		
Neutropenia, leucopenia, agranulocytosis	5	104
Febrile neutropenia	-	69
Anemia	3	158
Thrombocytopenia	4	73
Pancytopenia, bone marrow failure	2	10
Coagulopathy, disseminated intravascular coagulation, hemorrhagic diathesis	8	15
Hemolytic uremic syndrome, TTP	-	3
Leukocytosis	-	1
Metabolism and nutrition disorders		
Dehydration	7	294
Anorexia, failure to thrive, malnutrition, cachexia	1	243
Hypokalemia	-	34
Other electrolyte imbalance (Na+, Ca++, Mg++, phosphate)	-	86
Hyperglycemia, hypoglycemia	1	18
Psychiatric disorders		
Confusional state, mental status changes, disorientation	-	37
Anxiety	-	2
Depression	-	4
Nervous system disorders		
CVA, cerebral infarction, hemorrhagic stroke, TIA, hemiparesis, cerebral artery embolism	29	93
Headache	1	19
Neuropathy peripheral, paraesthesia	-	14

Lethargy, depressed consciousness	1	19
Aphasia	-	4
Coordination abnormal	-	1
Dizziness, vertigo	-	34
Syncope	-	17
Myasthenia gravis	-	1
Eye disorders		
Keratitis, keratoconjunctivitis sicca/dry eye, punctuate keratitis	-	12
Conjunctivitis	-	14
Ectropion	-	1
Uveitis, iridocyclitis	-	5
Vision blurred, visual disturbance, blindness	1	14
Corneal erosion/ulceration/perforation	-	6
Cardiac disorders		
Acute myocardial infarction, acute coronary syndrome, angina	15	57
Cardiac arrest, cardio-respiratory arrest	15	17
Cardiovascular disorder	2	2
Atrial fibrillation/supraventricular tachycardia/tachycardia	-	27
Cardiac failure acute, cardiac failure congestive, left ventricular failure, left ventricular systolic dysfunction	5	29
Bradycardia	1	4

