Vascular disorders		
Deep vein thrombosis, phlebothrombosis, thrombosis, jugular vein thrombosis	-	81
Hypotension, orthostatic hypotension	4	33
Vasculitis, vasculitis necrotizing	-	7
Peripheral embolism, embolism	-	9
Hypertension, hypertensive crisis	-	18
Peripheral ischemia	-	3
Respiratory, thoracic, and mediastinal disorders		
Pneumonitis, interstitial lung disease, bronchiolitis obliterans and organizing pneumonia (BOOP), lung infiltration, alveolitis	198	621
Dyspnea	34	218
Pulmonary embolism	17	107
Respiratory distress, acute respiratory distress syndrome	14	25
Respiratory failure, respiratory arrest	30	37
Anemic hypoxia, hypoxia	3	26
Hemoptysis, pulmonary hemorrhage	18	48
Epistaxis	-	20
Pharyngolaryngeal pain	-	3
Pulmonary fibrosis	1	21
Cough	1	20
Respiratory acidosis	1	1

Gastrointestinal disorders		
Diarrhea	16	873
Vomiting	2	332
Nausea	1	269
Gastrointestinal hemorrhage, melena, hematemesis, rectal bleeding	21	188
Mouth hemorrhage	-	2
Pancreatitis	1	24
Stomatitis, mouth ulceration, glossitis	-	98
Colitis, enterocolitis, cecitis	2	18
Abdominal pain, dyspepsia	2	103
Diarrhea hemorrhagic	-	4
Intestinal ischemia	1	4
Gastric Ulcer/Duodenal Ulcer	1	34
Esophagitis, gastritis	-	33
Intestinal perforation, gastrointestinal perforation, gastrointestinal ulcer perforation, diverticular perforation	14	37
Constipation	-	30
Dysphagia	-	27
Pneumoperitoneum	1	4
Hepatobiliary disorders		
Hyperbilirubinemia	-	51
Cholecystitis	-	8
Jaundice	-	8
Hepatic function abnormal, liver disorder	7	112
Hepatic steatosis	1	2
Hepatitis, hepatic failure, hepatotoxicity	15	31
Skin and subcutaneous tissue disorders		
Rash, dermatitis acneiform, exanthematous pustulosis, dermatitis, exanthema, acne, rash pustular, skin toxicity	-	698
Dermatitis exfoliative	-	31
Dermatitis bullous, blister	1	2
Stevens Johnson syndrome, erythema multiforme, skin necrosis	2	9
Dactylitis	-	2
Pruritus	-	14
Urticaria	-	8
Eczema	-	14
Hyperhidrosis	-	2
Paronychia	-	22
Palmar plantar erythrodysesthesia syndrome	-	14
Alopecia	-	2
Dry skin	-	8

Nail disorder, ingrowing nail, hair growth abnormal	-	8
Musculoskeletal and connective tissue disorders		
Muscular weakness	-	20
Joint swelling	-	1
Myalgia	-	9
Osteonecrosis	-	2
Renal and Urinary disorders		
Renal insufficiency, renal failure, nephrotic syndrome	15	96
Reproductive system and breast disorders		
Vaginal hemorrhage, menorrhagia	-	3
General disorders and administration site conditions		

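### Section 11.1: the safety stop counts only grade 3 or 4, so a related toxicity recorded only as fatal would not count

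*Combined protocol and SAP*

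**What the plan says.** All of the following is in Section 11.1 of the combined protocol and SAP, unless another section is named.

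- **Definition:** "Toxicity is defined as clinically significant, non-hematologic grade 3 or 4 toxicities at least possibly related to erlotinib".
- **Target:** the rate of that event is to be kept "related to erlotinib to be lower than 30% during the 1st 28 days".
- **Monitored parameter:** theta "is the proportion of any grade 3 or 4 clinically significant, non-hematologic toxicities at least possibly related to erlotinib".
- **Rule in words:** the trial ends if at any time "there is a more than 90% chance that the average rate of grade 3 or 4 non-hematologic adverse events is more than 30" percent.
- **Worked example:** "accrual will be stopped if 6 or more patients experience toxicity among the first 10 patients treated".
- **Table 1 caption:** "Stop accrual if the number of grade 3 or 4 non-hematologic adverse events is equal to or greater than indicated". The caption goes on to equate this with the number of grade 3 or 4 toxicities, set against the number of patients accrued.

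The prior is Beta(0.6, 1.4). Looks start at 10 evaluated patients and continue from there. Sections 6.2 and 10.2 name CTCAE version 4.0 as the grading scale.

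Section 2.1.1 describes a safety database with "approximately 9243 unique clinical study serious adverse events assessed as related to erlotinib in a total of 5846 patients". Its table has a column for fatal events; the row "Pneumonitis, interstitial lung disease, bronchiolitis obliterans and organizing pneumonia (BOOP), lung infiltration, alveolitis" shows 198 fatal of 621. Section 6.3 also mentions deaths from interstitial lung disease, gastrointestinal perforation and severe skin reactions. Section 10.4 sets out how deaths are reported and Section 11.2 how adverse events are tabulated. Neither contains a stopping rule.

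**The concern.** A toxicity stop should count the worst outcome of the kind it monitors. Here the grade range has an upper end. On a scale where death has its own grade, a patient whose related toxicity is recorded only as fatal falls outside the count, while a patient with a grade 3 event falls inside it. Nothing elsewhere in the protocol brings that death into the rule.

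At these sample sizes one patient can decide whether accrual stops. Whether a related death counts should therefore be settled in the text before the first look, not argued at an interim analysis with the case in hand.

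A smaller matter sits beside it. The rule in words and the Table 1 caption drop the conditions of clinical significance and relatedness. The caption compares a number of events with a number of patients. The 28-day window appears in the target sentence alone, although Section 3.0 lets treatment continue well beyond one cycle.

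**Working it through.** **Inputs (Section 11.1, with the maximum of 29 patients from Section 11.0):** prior Beta(0.6, 1.4); limit 0.3; stop if the posterior probability exceeds 0.90; looks from 10 patients onward.

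**Formula:** with x affected patients among n, the posterior is Beta(0.6 + x, 1.4 + n − x). Stop if Pr(theta > 0.3) > 0.90.

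**Step 1: reproduce Table 1.** The smallest x that crosses 0.90 matches all seven columns.

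| n | One short: x, posterior | Boundary: x, posterior |
|---|---|---|
| 10 | 5, 0.8798 | 6, 0.9625 |
| 13 | 6, 0.8651 | 7, 0.9500 |
| 15 | 7, 0.8927 | 8, 0.9597 |
| 18 | 8, 0.8833 | 9, 0.9514 |
| 21 | 9, 0.8761 | 10, 0.9443 |
| 23 | 10, 0.8993 | 11, 0.9549 |
| 26 | 11, 0.8940 | 12, 0.9498 |

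**Step 2: reproduce Table 2.** Exact recursion, one yes/no outcome per patient, looks after each patient from 10 to 28:

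| True rate | Exact stop probability | Table 2 |
|---|---|---|
| 0.2 | 2.9% | 3% |
| 0.3 | 21.0% | 21.5% |
| 0.4 | 58.1% | 57.5% |
| 0.5 | 88.5% | 88.5% |

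The differences are of the size expected from 10,000 simulations; at 0.3 the simulation standard error is √(0.21 × 0.79 / 10,000) = 0.4 percentage points. The printed figures are therefore sound, and they fit a count of patients.

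**Step 3: the fatal-only case.** Ten patients, five with related grade 3 or 4 toxicity and one whose related toxicity is recorded only as fatal.

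- As written, x = 5: Beta(5.6, 6.4), Pr(theta > 0.3) = 0.880. Continue.
- Death counted, x = 6: Beta(6.6, 5.4), Pr(theta > 0.3) = 0.962. Stop.

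The table in step 1 shows the same switch at every column.

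**Step 4: range under assumed rates.** The documents give no rate of fatal-only toxicity for this population, so these are illustrations only. Suppose 40% of patients have a related toxicity of grade 3 or higher. If none is fatal-only, the stop probability is 58.1%. If 2, 5 or 10 percentage points are fatal-only and left out, the rule sees 38%, 35% or 30%, and the stop probability is 50.2%, 38.4% or 21.0%.

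**Step 5: limit of the change.** If deaths count and five of 10 patients die of related toxicity with no other toxicity, x = 5 and the posterior is again 0.880. The trial continues.

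**The case against.** The strongest reply has four parts.

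*The fatal case rests on an assumption and may be rare.* The protocol does not say that death has its own grade, and a toxicity recorded at grade 3 or 4 before death may already count. This stands. The gap concerns fatal-only records, and their frequency cannot be taken from Section 2.1.1: 198 of 621 is a share of related serious events in other populations, not a rate per patient with AML.

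*Any integer boundary turns on one case.* True. Step 3 does not show that the boundary is faulty. It shows what is decided by leaving the death out.

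*Deaths do not go unseen.* Section 10.4 sends them to the IRB and the IND Office. That stands too, but reporting is not a stopping rule.

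*The other differences are shorthand.* A reader might infer that the definition and Table 1 contradict each other on relatedness, counting unit and window, or that Table 2 is wrong. The documents do not support that. The definition sentence gives neither a unit nor a window. The caption's own gloss points back to the defined term, the worked example counts patients, and both tables reproduce for one outcome per patient. The target sentence ties the 30% limit to 28 days, and theta is then compared with that limit, so one window is a natural reading. Stop probabilities can be computed for literal readings (for example, 16.7% instead of 2.9% at a 20% patient rate if events are counted and a quarter of affected patients have two), but they rest on assumed rates and a strained reading. What remains is wording to reconcile.

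**Conclusion.** The point holds as a cheap improvement to the safety stop. Followed literally, Section 11.1 can let accrual continue when a related death would have brought the count to the boundary: 0.880 against 0.962 at six affected patients of 10. This assumes that grade 5 means death and that the case is recorded only as fatal. How often it would occur is unknown.

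No printed number is wrong, and Table 2 correctly describes the rate of whatever event is counted. It would be too strong to say that the rule ignores all deaths, or that the change would turn it into a mortality safeguard. A death would weigh the same as a grade 3 event, and no look takes place before 10 patients.

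The relatedness, unit and window points are secondary. The evident intention is to count patients with at least one defined toxicity, each once. Only the window is left open enough to need a decision from the sponsor.

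**What to change.** In the definition, the target sentence, the definition of theta, the sentence restating the rule, and the Table 1 caption and row label, replace the grade range with *grade 3 or higher, including fatal*.

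In the same edit, use one event in all these places: *number of patients with at least one clinically significant non-hematologic toxicity of grade 3 or higher, including fatal, at least possibly related to erlotinib; each patient counted once*. Apart from the grade, this only makes explicit what the section already implies. The sponsor should also state whether the 28-day window applies to the count, and say so consistently.

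The cost is wording. The prior, the 0.90 cut-off, the sample size and Tables 1 and 2 do not change, because they depend only on a yes/no outcome per patient. The downside is a slightly higher chance of stopping if related deaths occur.
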